14.3.6 Subgroup Analyses of the Primary Endpoint

Subgroup analyses of the primary endpoint will be performed using the Bayesian repeated measures primary analysis model for the following subgroups:

- Use of concomitant medication (categorised into PD and autonomic dysfunction medication according to chapter 9). Two analyse will be performed: 1) where concomitant medication was already started up prior to baseline and continued after baseline, and 2) where concomitant medication was initiated or change in dose of existing medication after baseline
- Presence of MRI abnormalities at Screening supporting the diagnosis of MSA (i.e., 'yes' to at least one of the MRI abnormalities according to Screening MRI procedure)
- MSA sub-group (MSA-P and MSA-C)
- Pre-dose MSA positive result in the qualitative alpha-synuclein seeding aggregation assay (SAA), i.e., positive for alphaSyn seed amplification pattern predominantly found in subjects with MSA

14.3.7 Covariate Analyses of the Primary Endpoint

The effect of covariates on the primary endpoint will evaluated applying an ANCOVA to the change from baseline to Week 48 in UMSARS TS including the baseline UMSARS TS, Region, and CCI. The following covariates will be added and evaluated once at a time:

- age (categorized as <50yrs; 50-60; >60yrs)
- gender (female/male)
- race
- time-since-symptom onset (as yearly intervals)

- baseline plasma/CSF alpha-synuclein and CSF NfL (defined as baseline lower/middle/upper tertile)
- baseline disease severity according to category of CGI-S and UMSARS part IV (global disability score 1-5), and SE-ADL (defined as baseline lower/middle/upper tertile)

14.4 Analysis of the Secondary Endpoints

14.4.1 Analysis Methodology for the Key Secondary Endpoint

• For the key secondary endpoint, i.e., the changes in mUMSARS from baseline up to EoTDB, a Bayesian repeated measures model will be applied similar to the primary analysis.

Sensitivity analyses to the key secondary analysis will be set up similar to the sensitivity analyses described for the primary endpoints under section 14.3.5 Sensitivity Analyses of the Primary Endpoint(s).

14.4.2 Analysis Methodology for the Secondary Endpoint

- For the UMSARS Part I, UMSARS Part II and the aUMSARS, a similar Bayesian progression model and estimand strategy to the primary analysis will be applied.
- For remaining continuous secondary endpoints (e.g., clinical scales/assessments and MRI parameters), the change from baseline to EoTDB will be analysed using a restricted maximum likelihood (REML)-based mixed model for repeated measures (MMRM). The model will include the following: region, CCI and treatment (Lu AF82422 and placebo) as fixed factors, baseline as continuous covariate, treatment-by-week interaction and baseline-by-week interaction. An unstructured covariance structure will be used to model the within-patient errors. The Kenward-Roger approximation will be used to estimate denominator degrees of freedom. The analysis will be performed using all available observations (observed cases [OC] data) in the DBP. The estimated treatment differences between Lu AF82422 and placebo obtained at Week 48 will be estimated based on the least squares means for the treatment-by-week interaction in the MMRM model. Estimated treatment differences at Week 60 and 72 will be exploratory. In case of issues converging, a Toeplitz structure will be fitted instead.
- Categorical secondary endpoints will be evaluated using shift-tables evaluated at Week 48.
- Adjusted number of falls per individual per fall diary period in the DBP, according to the patient fall diary, will be analysed applying a MMRM as described above, if appropriate. Cause and consequence of falls will be evaluated descriptively.
- Time-to-wheelchair endpoint as assessed in the physical examination (first time point as 'full time user') following up to 72 weeks of treatment will be presented by a Kaplan-Meier plot and analysed applying a Cox proportional-hazards model. The model will be adjusted for stratification factors.
- Lu AF82422 plasma concentrations, CSF concentrations, and the CSF/plasma concentration ratios during treatment for all patients will be presented descriptively. A

population pharmacokinetics analysis (popPK) will also be performed and included in a separate reported.

- Absolute values and changes from baseline to EoTDB in blood and CSF biomarkers will be analysed descriptively (i.e., NfL, t-tau, truncated alpha synuclein). A MMRM will be applied for the changes from baseline to EoTDB. If required, a log transformation will be applied for normalization.
- TE of Lu AF82422 to α -synuclein in plasma and CSF will be presented descriptively as 'free' α -synuclein, 'total' α -synuclein and ratio of 'free' to 'total' α -synuclein. In addition, TE will be plotted vs. concentration of Lu AF82422 to characterize the relationship.
- Results from the semi-quantitative alpha synuclein seeding assay (SAA), i.e., the SD50 representing the time to reach 50% max, will be presented descriptively over time.
- Gait and balance parameters derived from the sensor based FeetMe® device will primarily be analysed descriptively for the SBS. a MMRM model, like the one described above for continuous secondary and exploratory endpoints, will be applied to the change from baseline. Correlation to the key progression markers, that is the UMSARS scores and MRI parameters, will be explored graphically using scatterplots.

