#### 17.9 Efficacy Analyses

# 17.9.1 General Efficacy Analysis Methodology

Unless otherwise specified, all the efficacy analyses for the DBP will be based on the FAS. All endpoints will be presented with descriptive statistics and the one-sided 95% confidence intervals for both absolute values and change from baseline. Histograms will be explored and presented for the UMSARS scores observed cases; otherwise only in case of compromising findings for the secondary endpoints.

Since the primary, key secondary and selected secondary analyses for the UMSARS scores will be performed in a Bayesian framework, the success threshold for the Bayesian posterior probability of superiority relative to placebo will be calibrated through simulations to correspond to a significance level of 5% evaluated one-sided. For the frequentist analyses, the significance level will be 5%, which will be applied one-sided.

A testing strategy will be applied including the primary analysis on UMSARS TS and the key secondary analysis on mUMSARS to protect the type I error for these analyses. Further details in the section 17.9.4, Testing Strategy.

Efficacy analyses for the OLE will be exploratory based on the OLES. All patients in the OLE will receive active treatment. However, patients receiving placebo in the DBP and hence switching treatment will be defined and handled as a separate group.

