## 17.9.6 Analysis of the Secondary Endpoint(s)

For secondary endpoints in the DBP the following methodology will be applied:

• For the secondary endpoints UMSARS Part I and UMSARS Part II up to EoT, a Bayesian repeated measures model will be applied similar to the primary analysis.

- For remaining continuous secondary endpoints (for example, clinical scales/assessments and MRI volumetric parameters), a Mixed Model for Repeated Measurements (MMRM) will be applied to the changes from baseline up to Week 72. If required, a log transformation will be applied for normalization. The model will contain the following effects: baseline score, treatment, visit, baseline blood NfL, Region, treatment\*visit and baseline score\*visit as fixed effects and subject as random effect. Treatment estimates will be derived for each subsequent visit. The primary comparison will be at Week 48, whereas Week 72 will be exploratory. Initially, an unstructured covariance matrix will be fitted. In case of issues converging, a Compound Symmetry structure will be used.
- All categorical secondary endpoints will be analyzed applying a logistic regression. Treatment effect evaluated at Week 48 will be primary.
- Number of falls per individual per fall diary period, according to the patient fall diary, will be analyzed applying a negative binomial regression model.
- Additional time-to-event secondary and exploratory endpoints following 48 weeks and 72 weeks of treatment will be analyzed applying a Cox proportional-hazards model. Week 48 will be primary.
- Lu AF82422 plasma concentrations, CSF concentrations, and the CSF/plasma concentration ratios during treatment for all patients will be presented descriptively. The data will be included in a separately reported population PK analysis.
- Absolute values and changes from baseline up to Week 48 and Week 72 in blood biomarkers and Week 48 in CSF biomarkers will be analyzed descriptively. For selected parameters, a MMRM will be applied for the changes from baseline to EoT. If required, a log transformation will be applied for normalization.
- TE of Lu AF82422 to  $\alpha$ -synuclein in CSF will be presented descriptively as "free" synuclein, "total"  $\alpha$ -synuclein and ratio of "free" to "total"  $\alpha$ -synuclein.

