14.2 General Efficacy Analysis Methodology

Unless otherwise specified, all efficacy analyses will be based on the FAS for the observed case (OC) data.

For endpoints analysed in the Bayesian framework, the success threshold for the Bayesian posterior probability of superiority relative to placebo [Prob(θ <1)] has been calibrated using simulations to correspond to a significance level of 5% applied one-sided. By doing so a success threshold of 0.975 has been identified which will be used to evaluate the primary endpoint and remaining endpoints evaluated by the Bayesian progression model. A burn-in of 1000 samples will be used for the Bayesian analysis.

All statistical tests of the secondary efficacy endpoints will be presented two-sided on a 5% significance level.

A testing strategy will be applied including the primary analysis on UMSARS TS and the key secondary analysis on mUMSARS to protect the type I error on an overall one-sided 5% significance level for these analyses. Further details to be found in chapter 15.

For analysis of exploratory efficacy data collected in the open-label extension, the original placebo patients will be presented as a separate group and hence there will be no pooling of treatment groups.

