14.3 Analysis Methodology for the Primary Endpoint

14.3.1 Primary Analysis of the Primary Endpoint

The primary efficacy analysis following up to 72 weeks of treatment will be based on a Bayesian repeated measures model, also referred to as a Bayesian functional-impairment

progression model (BFPM), of the changes from baseline in the UMSARS TS. The BFPM incorporates the following aspects:

- Repeated measures for the change from baseline in the UMSARS TS score over the recurring 72-week's visit schedule
- Piece-wise linear rate of progression per 12-week time interval. However, does not require equally spaced intervals between observations. Time modelled continuously
- Patient-level random effect in rate of progression
- Proportional treatment effect, θ, for slowing of disease progression rate when treated relative to placebo. In particular, if θ<1, the active treatment slows the rate of progression relative to placebo. If θ>1, the active treatment increases the rate of progression relative to placebo. If θ=1, the rate of progression of UMSARS TS is the same for both active treatment and placebo
- Fixed multiplicative covariate effects in the increase or decrease in the overall rate of
 progression of UMSARS TS for categorized CCI

and region (US and Japan) common across all visits

- Prior distributions for model parameters selected in a conservative and non-informative manner using relatively large outcome spaces
- The primary analysis considers only actual observations and does not impute missing data

Let change from baseline in the UMSARS TS at visit *j* for subject *i* be labelled $Y_{i,j}$, $i = 1, ..., N, j = 1, ..., J_i$ where there are J_i total post-baseline visits for subject *i*. Change from baseline will be modelled as piece-wise linear with time intervals, k = 1, ..., K, defined every 12 weeks. Let $X_{i,j,k}$ be the exposure (time since baseline in weeks) for subject *i* at visit *j* during the time interval *k*. The MSA progression model is:

$$Y_{i,j} \sim N(\mu_{i,j}, \sigma_{t(i)}^2); i = 1, ..., N; j = 1, ..., J_i$$

$$\mu_{i,j} = 0 + \sum_{k=1:K} \left(\beta_k + \beta_{k,i} \right) * (X_{i,j,k}/12) * \theta_{t(i)} * \exp\left(\delta_{g(i)} + \eta_{r(i)} \right)$$

where each parameter is defined below and the prior distribution for the parameter is given:

 β_k : Mean expected change from baseline over each 12-week interval

$$\beta_k \sim Norm(0, 10^2)$$
; $k = 1, \dots, K$

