14.6 Analysis of Exploratory Endpoints

For exploratory endpoints the following methodology will be applied:

- For continuous exploratory endpoints, a MMRM will be applied for observed data (OC), using observed data from the Withdrawal Visit for patients dropping out (for other reasons than death), if available. The model will contain the following effects: baseline score, treatment, visit, CCI, Region, treatment*visit and baseline score*visit as fixed effects and subject as random effect. The main comparison will be at Week 48. Initially, an unstructured covariance matrix will be fitted. In case of issues converging, a Toeplitz structure will be used.
- Time-to-event exploratory endpoints up to EoTDB will be analysed applying a Cox proportional-hazards model.

- Number of falls per individual according to the sensor-based PAMSys device will be analysed descriptively including data from the pre-defined periods only.
- Target engagement and biofluid markers in general will primarily be explored graphically. If applicable, relevant efficacy endpoints will be evaluated especially for patients obtaining target engagement.
- The analysis of Screening and Exit semi-structured, qualitative interviews will be prespecified in a specific Qualitative Analysis Plan (QAP). Whenever a combined quantitative and qualitative approach is considered, a dedicated Mixed Method QAP will be developed.

Open-label extension (OLE)

• All continuous endpoints following treatment extension will primarily be analysed descriptively. In addition, a MMRM will be applied similar to the one described above to the change from the original baseline (DB baseline), where patients originally treated with pbo will be kept as a separate group. No formal testing will be applied.

15 Testing Strategy

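### The MMRM fallback to an unqualified Toeplitz covariance would understate the Week 48 standard error if variance grows with time

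*SAP*

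**What the plan says.** SAP 14.4.2 analyses the continuous secondary endpoints outside the Bayesian model with a REML-based MMRM. The first choice is clear: "An unstructured covariance structure will be used to model the within-patient errors". The fallback is "In case of issues converging, a Toeplitz structure will be fitted instead". For inference, "The Kenward-Roger approximation will be used to estimate denominator degrees of freedom"; no robust standard error is mentioned.

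SAP 14.3.5 repeats this specification and fallback for the UMSARS TS sensitivity MMRM, and 14.4.1 carries the sensitivity analyses over to mUMSARS. SAP 14.6 also falls back to Toeplitz for the exploratory endpoints; its model description reads "subject as random effect. The main comparison will be at Week 48. Initially, an unstructured covariance matrix will be fitted". In all three sections the comparison that counts is at Week 48.

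The SAP does not say whether Toeplitz means common or visit-specific variances, and the SAS code in Appendix II is blacked out. Protocol 17.9.6 names a different fallback: "In case of issues converging, a Compound Symmetry structure will be used"; 17.9.7 does the same. SAP section 23 does not list the change.

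The primary progression model (SAP 14.3.1) includes a "Patient-level random effect in rate of progression".

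The documents differ on sidedness. SAP 14.2: "All statistical tests of the secondary efficacy endpoints will be presented two-sided on a 5% significance level". Protocol 17.9.1: "For the frequentist analyses, the significance level will be 5%, which will be applied one-sided".

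**The concern.** Without a qualifier, Toeplitz normally means one variance shared by all visits, with correlation depending only on lag. If patients progress at different rates, their changes from baseline spread out over time. A pooled variance is then too large at early visits and too small at late ones, Week 48 included. Kenward-Roger is a small-sample adjustment within the assumed covariance; it does not repair a covariance of the wrong shape. Intervals for the Week 48 contrast would be too narrow, and nominal 5% tests would reject too often, in just those analyses where the first-choice model had failed.

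**Working it through.** **1. The plan's own figures.** The plan gives no error rate for the fallback, so there is none to reproduce. Its one quantitative anchor is about 75% power for 40% slowing, one-sided 5%, 40:20 patients (SAP section 21). That back-solves to a standardised effect of (1.645 + 0.674) × √(1/40 + 1/20) ≈ 0.64, which says nothing about variance by visit. No visit-specific SD is readable for any MMRM endpoint.

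**2. Variance implied by the SAP model for UMSARS.** In 14.3.1 each patient's random rate multiplies time/12. For a patient whose treatment and covariate multipliers are 1,

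Var(change at week t) = σ² + σ_β²(t/12)².

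The direction comes from the SAP; the size does not. As an illustration, assume σ/σ_β = 2. In units of σ_β² the variances at Weeks 12, 24, 36, 48, 60 and 72 are 5, 8, 13, 20, 29 and 40. The SD doubles from Week 12 to Week 48 (√(20/5) = 2).

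**3. Effect of pooling, by hand.** Weight the visits 1, 1, 1, 1, 0.5 and 0.25, from the planned 50% with 60-week and 25% with 72-week data, ignoring drop-out. The pooled variance is (5 + 8 + 13 + 20 + 14.5 + 10)/4.75 = 14.8. The SE ratio at Week 48 is about √(14.8/20) = 0.86.

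**4. From SE ratio to error rate.** If the reported SE is k times the true one, the rejection rate is about 2[1 − Φ(1.96k)] two-sided and 1 − Φ(1.645k) one-sided. At k = 0.85 this gives 9.6% and 8.1%.

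**5. Simulation of the fallback.** REML with common-variance Toeplitz; treatment-by-week, baseline-by-week, region and a binary stratum; 40:20 patients; 20% drop-out; the planned follow-up mix; about 930 null trials per scenario; t with 55 df in place of Kenward-Roger. At a 9% rate the Monte Carlo SE is √(0.09 × 0.91/930) ≈ 0.9 points.

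| Assumed pattern | SE ratio, Week 48 | Two-sided 5% | One-sided 5% |
|---|---|---|---|
| Six visits, constant variance (control) | 1.02 | 3.8% | 4.6% |
| Six visits, random slope, σ/σ_β 0.5 to 6 | 0.85–0.93 | 6.3–9.5% | 5.9–8.5% |
| Six visits, random walk plus error | 0.83–0.90 | 7.9–9.9% | 6.8–8.0% |
| Four visits (MRI schedule) | 0.79–0.87 | 8.5–11.7% | 6.7–8.8% |
| Three visits (SE-ADL, COMPASS Select Change, EQ-5D VAS) | 0.85–0.93 | 6.2–9.2% | 5.3–6.9% |

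The control shows no excess, so the excess elsewhere comes from variance growth. At σ/σ_β = 2 with six visits the ratio is 0.853, in line with step 3.

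**6. Same data patterns, heterogeneous Toeplitz** (about 375 trials each).

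- Three visits, σ/σ_β 1 and 2: SE ratio 0.96–0.97 and two-sided rejection 5.4–5.7%, against 0.85–0.88 and 8.7–9.2% with a common variance.
- Six visits, σ/σ_β = 2: 0.94 and 7.7% (Monte Carlo SE about 1.4 points), against 0.853 and 9.5%.

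**7. Covariance parameters.** With v visits, unstructured needs v(v+1)/2, heterogeneous Toeplitz 2v − 1 and common-variance Toeplitz v.

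| Visits | Unstructured | Heterogeneous Toeplitz | Toeplitz |
|---|---|---|---|
| 6 | 21 | 11 | 6 |
| 4 | 10 | 7 | 4 |
| 3 | 6 | 5 | 3 |

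**The case against.** The strongest reply is that the fallback may rarely be used. A reader might infer from 21 covariance parameters and about 12 patients at Week 72 (60 × 25% × 80%, about 4 on placebo) that the unstructured fit will probably fail. That was not borne out. In simulated six-visit trials of this size (slope SD 1.7, error SD 3), the unstructured fit converged in about 96% of 222 fits and rejected 3.2% at two-sided 5%. With a 4% fallback rate at about 9.5%, the overall rate is roughly 0.96 × 3.2% + 0.04 × 9.5% ≈ 3.5%. This was not run in SAS or with Kenward-Roger, so it does not settle the frequency, but likely failure cannot be claimed. Many endpoints in 14.4.2 also have only three or four post-baseline visits (SAP 24.2.1, 24.2.2), where failure is less likely.

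Two further points stand. The common variance is the usual reading of unqualified wording, and the blacked-out code might specify otherwise. And the SAP implies variance growth only for UMSARS; for bounded 0 to 4 global scales, the VAS or MRI it is plausible but undemonstrated.

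A reader might also take the MMRM as the main check on the primary analysis. SAP 14.3.5 does not say so. It lists the MMRM beside imputation analyses, a joint-rank analysis, a sceptical prior and a spline model that is also evaluated at Week 48, with unstructured covariance and no Toeplitz fallback.

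None of this defends a common variance once the fallback is in use.

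**Conclusion.** The point holds as a conditional one. If the unstructured model fails, if Toeplitz is fitted with one variance, and if variance grows with time, the Week 48 SE is about 7% to 21% too small. The SAP's two-sided 5% test then rejects about 6% to 12%, and the protocol's one-sided 5% test about 5% to 9%. These ranges rest on assumed variance patterns and on a t reference in place of Kenward-Roger. A single figure, such as 15% too small with 9% rejection, describes one assumption (SD about doubling from Week 12 to Week 48) and is not a property of the plan.

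The primary and key secondary conclusions are not at risk: both are decided by the Bayesian model under the fixed sequence in SAP 15.2. What is affected is the sensitivity MMRM and the secondary and exploratory MMRMs outside that sequence. A reader might also infer from 14.6 that a random intercept is stacked on an unstructured matrix, which would not be identifiable. The phrase may only name the repeated-measures subject, and without the code this cannot be decided. This is a cheap improvement, not a defect that threatens the trial's main result.

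**What to change.** In SAP 14.3.5, 14.4.2 and 14.6, name heterogeneous Toeplitz, with a separate variance for each visit, as the first fallback, and keep Kenward-Roger. The cost is a few words and one covariance option, a few more parameters than plain Toeplitz (11 against 6 with six visits), and slightly wider intervals. It removes most of the bias, but not all with six visits: about 7.7% in simulation. A compulsory sandwich standard error is not proposed; at 60 patients it is debatable and sits awkwardly with the planned Kenward-Roger method.

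Optional clarifications: state in 14.6 that the subject term identifies the repeated-measures unit and is not an extra random intercept, and list the move away from the protocol's compound symmetry fallback in SAP section 23.

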  - Participant-level random effects for the rate of UMSARS progression across visits
  - Fixed multiplicative treatment effect, θ, for increase or decrease in the overall rate of UMSARS progression of Lu AF82422 relative to placebo common across all visits. In particular, if θ<1, the active treatment slows the rate of progression of UMSARS relative to placebo. If θ>1, the active treatment increases the rate of progression of UMSARS relative to placebo. If θ = 1, the rate of progression of UMSARS is the same for both active treatment and placebo
  - Fixed multiplicative covariate effects in the increase or decrease in the overall rate of progression of UMSARS for CCI and Japan common across all visits
  - Prior distribution for model parameters selected in a conservative and non-informative manner using relatively large outcome spaces
  - Sensitivity analyses to cover model assumptions and handling of missing data applying different imputation strategies
- · Analysis of the key secondary, secondary and exploratory endpoints in the DBP:
  - · All secondary and exploratory analyses will be based on the FAS.
  - For the key secondary endpoint, that is, changes in mUMSARS from baseline up to EoT, a Bayesian repeated measures model will be applied similar to the primary analysis.
  - For changes in UMSARS Part I and UMSARS Part II scores up to EoT, a Bayesian repeated measures
    model will be applied similar to the primary analysis.
  - All remaining continuous secondary and exploratory endpoints (for example, clinical scales/assessments
    and MRI parameters) will be analyzed applying a Mixed Model for Repeated Measurements (MMRM) to
    the changes from baseline up to Week 72. If required, a log transformation will be applied for normalization. Treatment estimates will be derived for each subsequent visit. The primary comparison will be at
    Week 48, whereas Week 72 will be exploratory.
  - All categorical secondary and exploratory endpoints following 48 weeks and 72 weeks of treatment will be analyzed applying a logistic regression model. Week 48 data will be primary.
  - Number of falls per individual per fall diary period, according to the patient fall diary, will be analyzed applying a negative binomial regression model. A similar model will be applied to the falls collected by the sensor-based PAMSys device, if applicable, including data from the pre-defined periods only.

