14.1 Overview of Planned Efficacy Analyses in the DB-Period

An overview of all planned efficacy analyses is provided in Panel 2. Where relevant, the analyses will be presented by visit. Endpoints related to as 'disease progression' (primary and selected secondary endpoints) will be analysed using a 'Bayesian' progression model; remaining continuous variables will be analysed applying a MMRM in a Frequentist framework, where stated.

Variables	Туре	Priority	Description
UMSARS TS	1	1	Sum of UMSARS Part I+II items (Primary)
mUMSARS score	1	2	Sum of Part I items with respond option 0 and 1 collapsed
UMSARS Part I score	1	3	Sum of UMSARS Part I items
UMSARS part II score	1	3	Sum of UMSARS Part II items
aUMSARS score	1	4	Sum of UMSARS Part I+II selected items - PI: 1,3,4,7,8 & PII: 2,6,8,11,14
SE-ADL score	2	3	Schwab and England Activities of Daily Living scale: sum of items
CGI-S score	2	3	Global impression severity, Clinical: sum of items
PGI-S score	2	3	Global impression severity, Patient: sum of items
OGI-S score	2	3	Global impression severity, Observer-reported: sum of items
COMPASS select change	2	3	Composite autonomic symptom: a score for each domain
UMSARS part III items	2	4	Heart rate, sys/dia blood pressure; individual items
UMSARS part III items	3	4	orthostatic symptoms; individual item
UMSARS part IV item	3	3	Global disability: UMSARS single item
UMSARS part I items	3	3	Disease milestones: Speech, swallowing, walking and falls; UMSARS Part I single items
Patient fall diary	3	3	Disease milestones: Frequency, cause and consequence of falls; patient dairy derived
Use of wheelchair	4	4	Disease milestones: Wheelchair – time to full time user; according to physical examination
PamSys digital device	3	4	Disease milestones: Frequency of Falls; PamSys derived
FeetMe digital device	2	4	Disease milestones: gait parameters; FeetMe derived
EQ-5D-5L items	3	3	Health-related quality of life: domain scores
EQ-5D-5L VAS score	2	3	Health-related quality of life: VAS score
MRI, volumetric (vMRI)	2	3	volume in ROIs (e.g., caudate nucleus, putamen, striatum, pons, brain stem, grey matter and cerebellum)

Panel 2 Overview of Planned Efficacy Analyses (DB-Period)

Study 18331A – Statistical Analysis Plan

Variables	Туре	Priority	Description
MRI, diffusivity (DTI MRI)	2	4	Mean diffusivity in ROIs (e.g., caudate nucleus, putamen, globus pallidus, pons, cerebellar cortex and white matter and middle cerebellar peduncle, both FA and MD)

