Blood biomarkers	2	3, 4	neurofilament light (NfL) concentrations [2], 'free' and 'total' α -synuclein [3]
CSF biomarkers	2	4	concentrations of t-tau, NfL, 'free' and 'total' α -synuclein, pathological species of α -synuclein
MRI, arterial spin (ASL)	2	4	Mean Cerebral blood flow in ROIs (e.g., putamen and cerebellum)
Type: 1 = continuous_Bayes; 2 = continuous_Other; 3 = categorical; 4 = time to event; Priority: 1 = Primary; 2 = Key Secondary; 3 = Secondary; 4 = Exploratory			

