20 Interim Analyses

No interim analyses will be conducted for this study.

21 Sample Size Considerations

The 18331A sample size has been selected to ensure an appropriate power to detect a 40% slowing in MSA progression in the Lu AF82422 CO dose group compared to the placebo group on a 5% significance level evaluated 1-sided. Applying a repeated measures model with proportional treatment effect, yields an approximate 75% power when having N=60 patients allocated 2:1 in favour of Lu AF82422 treatment (i.e., 40 on Lu AF82422 *versus* 20 on

Study 18331A - Statistical Analysis Plan

placebo) when using the NLMIXED procedure for simulating in SAS[®]. To account for differences in treatment duration due to the study design, approximately 50% of the patients are expected to contribute with 60 weeks data and 25% of the patients with full 72 weeks data. On top, an overall 20% drop-out rate has been accounted for. For comparison, it is expected that the frequentist repeated measures model used for simulation is quite similar in relation to performance to the primary Bayesian repeated measures model.

22 Statistical Software

The statistical software used will be SAS[®], version 9.4 or later, and R, version 3.12 or later, respectively. For R, the packages Jags and Coda would be required to run the MCMC procedures.

23 Changes to Analyses Specified in the Protocol

• According to SAP section 16.1.4, TEAEs will be assigned to two periods rather than four periods as described in Protocol section 16.10.1, the reason being that the safety follow up periods following the DBP and the OLEP, respectively, will be part of the reporting periods rather than individual periods. In this way the first safety follow up period following the DBP will be reported as part of the DBP, and the safety follow up period following the OLEP will be reported as part of the OLEP.

24 Details on Data Handling

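### SAP 14.4.2 reduces UMSARS Part IV, four UMSARS Part I items and the EQ-5D-5L items to Week 48 shift tables, dropping the model-based treatment comparison in the protocol without declaring it

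*SAP*

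**What the plan says.** Protocol 17.9.6: "All categorical secondary endpoints will be analyzed applying a logistic regression. Treatment effect evaluated at Week 48 will be primary". The protocol synopsis, under Statistical Methodology, agrees: "All categorical secondary and exploratory endpoints following 48 weeks and 72 weeks of treatment will be analyzed applying a logistic regression model". Protocol 17.9.6 also assigns the remaining continuous secondary endpoints to an MMRM. It names clinical scales as examples and makes Week 48 the primary comparison.

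SAP 14.4.2 says of the categorical secondary endpoints: "Categorical secondary endpoints will be evaluated using shift-tables evaluated at Week 48". It names no model, test or effect measure for them. Its MMRM bullet is limited to continuous endpoints.

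SAP Panel 2 (section 14.1) decides which endpoints are affected. Its key reads "Type: 1 = continuous_Bayes; 2 = continuous_Other; 3 = categorical; 4 = time to event". Three rows matter here, all coded type 3 and priority 3 (secondary):

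- UMSARS Part IV: "Global disability: UMSARS single item"
- UMSARS Part I items: "Disease milestones: Speech, swallowing, walking and falls; UMSARS Part I single items"
- EQ-5D-5L items: "Health-related quality of life: domain scores"

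SAP section 23, on changes from the protocol, has one entry, about adverse-event periods: "TEAEs will be assigned to two periods rather than four periods".

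**The concern.** A shift table sets baseline category against Week 48 category within each arm. It gives no contrast between arms, no interval, and no adjustment for baseline or the stratification factors. SAP chapter 6 itself places shift tables under descriptive statistics.

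Efficacy on global disability is a stated secondary objective, and UMSARS Part IV is its only endpoint. Under the SAP that objective would be reported without any estimate of the treatment effect. The same is true of the four Part I items and the five EQ-5D-5L items. Readers would compare cells by eye across arms of unequal size (2:1), and any contrast computed after unblinding would be post hoc. SAP 14.2 states how tests of secondary endpoints will be presented, but no test exists for these ten.

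**Working it through.** The plan states no figure on this point, so the check is a comparison of texts followed by a feasibility calculation.

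**1. What each endpoint gets**

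| Endpoint | SAP Panel 2 | Protocol | SAP 14.4.2 |
|---|---|---|---|
| UMSARS Part IV | type 3, secondary | model, Week 48 comparison | shift table |
| Part I speech, swallowing, walking, falls | type 3, secondary | model, Week 48 comparison | shift table |
| EQ-5D-5L items | type 3, secondary | model, Week 48 comparison | shift table |
| Fall diary frequency | type 3, secondary | negative binomial model | MMRM if appropriate |
| Time to wheelchair | type 4, exploratory | Cox model | Kaplan-Meier and Cox |
| EQ-5D VAS | type 2, secondary | MMRM | MMRM |
| CGI-S, PGI-S, OGI-S | type 2, secondary | MMRM | MMRM |

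The protocol column for the first three rows says only that there is a model, because the protocol does not itself call these endpoints categorical. It defines them as changes from baseline in scores. In its exploratory objectives (Panel 4) it groups Part I items 1, 2, 7 and 8, Part IV and EQ-5D-5L as clinical scales. Read as categorical they get logistic regression; read as clinical scales they get the MMRM. Both carry a treatment comparison at Week 48, so a model is lost either way.

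**2. Is it a version effect?** The protocol's table of major changes since its previous edition shows no change to the logistic regression, and the current text keeps it. Section 23 of the SAP does not list its removal.

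**3. Is it explained by the type of scale?** CGI-S, PGI-S and OGI-S are each a single rating with five levels, 0 to 4. Part IV is a single rating with five levels, 1 to 5. The first three are typed continuous and modelled; Part IV is typed categorical and is not. The SAP gives no reason.

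**4. What would a restored analysis deliver?** Inputs: 40 active and 20 placebo patients (protocol synopsis), and 20% overall drop-out (protocol 17.12), giving 40 × 0.8 = 32 and 20 × 0.8 = 16. Assumption: a binary outcome of worsening by at least one category, with a common rate p between 0.3 and 0.7. The documents give no such rate.

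SE(log OR) = √[1/(n₀p(1−p)) + 1/(n₁p(1−p))]; 95% CI factor = exp(1.96 × SE).

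- 20 vs 40, p = 0.5: √(1/5 + 1/10) = 0.548, factor 2.93
- 20 vs 40, p = 0.3 or 0.7: √(1/4.2 + 1/8.4) = 0.598, factor 3.23
- 16 vs 32, p = 0.5: √(1/4 + 1/8) = 0.612, factor 3.32
- 16 vs 32, p = 0.3 or 0.7: √(1/3.36 + 1/6.72) = 0.668, factor 3.70

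Power is low. Assume a 40% relative reduction from placebo worsening rates of 0.3, 0.5 and 0.7. Two-sided 5% power is then 0.195, 0.330 and 0.536 with 20 vs 40, and 0.167, 0.275 and 0.445 with 16 vs 32.

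**5. How large a model can the data carry?** A five-level proportional-odds model with baseline as a category needs 4 thresholds + 1 treatment + 4 baseline + 2 NfL + 1 region = 12 parameters on about 48 to 60 patients. (The SAP's primary model codes NfL as low, high and missing.) With baseline as one linear term the count is 4 + 1 + 1 + 2 + 1 = 9. Collapsing to three outcome levels brings it to 2 + 1 + 1 + 2 + 1 = 7.

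**The case against.** The best defence is that these are single items in a 60-patient phase II trial, where a descriptive display is reasonable and a rich ordinal model could separate or fail to converge. No trial decision rests on them: only UMSARS TS and mUMSARS are in the testing hierarchy (SAP 15.2). The four Part I items already contribute to the modelled UMSARS TS, Part I and mUMSARS scores, and three of them (speech, walking, falls) also enter aUMSARS. SE-ADL and CGI-S, which cover dependency and global severity, keep MMRMs.

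Much of this stands. It limits the importance of the point and argues for a small model. It does not remove the point, because low power is a reason the SAP could have given and did not, and the protocol still promises a model.

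A reader might also infer that shift tables would show only patients who attended the Week 48 visit. The SAP does not support that. It maps withdrawal and unscheduled assessments to analysis weeks (24.2), its broad UMSARS window for Week 48 runs from day 295 to day 378 (Panel 16), and it sets EQ-5D domains to the worst level at the visit after death (Panel 7). Nor does spreading 32 and 16 patients evenly over 25 cells say much. Screening Part I scores are capped at 16, so baseline categories are likely to cluster.

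**Conclusion.** The point holds in a limited form. Ten single-item secondary endpoints (1 + 4 + 5) have a Week 48 model in the protocol and none in the SAP, and the change is undeclared. The gap is complete for global disability and partial for disease milestones and quality of life.

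Two stronger readings go too far. One is that the disease-milestone objective also has no treatment-effect estimate. In fact fall-diary frequency keeps an MMRM if appropriate, and exploratory time to wheelchair keeps a Cox model. The other is that the SAP certainly replaced logistic regression. The categorical label comes only from SAP Panel 2, so the lost analysis may equally be the MMRM for clinical scales.

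This is worth correcting but does not threaten the primary or key secondary conclusions. The interval factors of about 2.9 to 3.7 rest on assumed worsening rates of 30% to 70%, and the upper end also on the full 20% drop-out occurring by Week 48. The SAP's code appendices are redacted, so this rests on the SAP text alone.

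**What to change.** In SAP 14.4.2, prespecify a between-arm analysis at Week 48 for UMSARS Part IV, the four Part I items and the EQ-5D-5L items. Two forms would do:

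- the protocol's logistic regression, for example on worsening by at least one category; or
- a proportional-odds model with treatment, baseline score as a single linear term and the stratification factors, with a rule fixed in advance for collapsing sparse categories.

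Report the odds ratio with its 95% CI as supportive, outside the testing hierarchy. Keep the shift tables as displays. List in section 23 any departure from the protocol that remains, with the reason; if a descriptive-only analysis is preferred for some items, that is where to justify it.

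No new data are needed. The cost is a few model outputs and some SAP wording. The downside is wide intervals and possible sparse-data or convergence problems, which the collapsing rule should anticipate.
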